#### Number of Patients (Planned):

Phase 1: 43 patients were enrolled and dosed. Enrollment to Phase 1 is closed.

Phase 2a: Approximately 240 patients.

Total: Up to 283 patients dosed for the entire study

#### Diagnosis and Main Criteria for Inclusion:

##### Phase 1 Cancer-Specific Inclusion Criteria

1. Patient must have a histologically confirmed diagnosis of 1 of the following:
  - CLL/SLL
  - B-cell non-Hodgkin lymphoma, any of the types specified below, all with relapsed or refractory disease:
    - Diffuse Large B-cell lymphoma (DLBCL)
    - Follicular lymphoma (FL)
    - Mantle cell lymphoma (MCL)
    - Mucosa Associated Lymphoid Tumor (MALT)
    - Marginal zone lymphoma (MZL)
    - Lymphoplasmacytic lymphoma (LPL)

##### Phase 1 General Inclusion Criteria

1. Patient has failed at least 1 prior established treatment regimen (e.g., progressed during, or refractory to), and no other standard therapy exists for that patient, or patient is intolerant of existing standard therapy or is not a candidate for such standard therapy.
2. Patient must have an Eastern Cooperative Oncology Group (ECOG) Performance Score of 0 or 1.
3. Patient must be 18 years or older, of either sex, and of any race.
4. Patient (and/or parent/guardian for patients who otherwise are unable to provide independent consent) must be willing to give written informed consent and be able to adhere to dose and visit schedules.

5. Female patients of childbearing potential and male patients must agree to abstain from sexual intercourse or to use an effective method of contraception during the study and for 90 days following the last dose of protocol therapy (examples of effective methods of contraception include oral contraceptives or double barrier methods such as condom plus spermicide or condom plus diaphragm).
6. Patient must have adequate bone marrow reserve as evidenced by an absolute neutrophil count (ANC)  $\geq 1,000/\mu\text{L}$  AND platelet count  $\geq 75,000/\mu\text{L}$ .
7. Patient must have adequate renal function as evidenced by a serum creatinine level  $\leq 1.5 \times$  upper limit of normal (ULN) or a calculated creatinine clearance  $> 60$  mL/min.
8. Patient must have adequate hepatic function as evidenced by a serum bilirubin level  $\leq 2.0$  mg/dL AND serum aspartate aminotransferase/alanine aminotransferase (AST/ALT) levels  $\leq 2.5 \times$  the ULN for the reference laboratory. Serum bilirubin must be  $\leq 2.5$  mg/dL when increase is clearly documented as due to Gilbert's syndrome.

### Phase 2a Cancer-Specific Inclusion Criteria

Patient must have a histologically confirmed diagnosis of 1 of the following:

Note: Definitions for "relapsed" and "refractory" disease are provided in [Table 3](#).

- FL Grade 1 to 3A, with relapsed or refractory disease.
- Aggressive NHL (aNHL), defined as DLBCL, FL Grade 3B, MCL, and transformed NHL with relapsed disease.
- CLL/SLL, with relapsed or refractory disease.
- PTCL, with relapsed or refractory disease.
- CTCL with relapsed or refractory disease. Only CTCL patients with MF/SS are allowed.

Patients who received any BCR pathway inhibitor (e.g., BTK inhibitors such as ibrutinib, or PI3 Kinase inhibitors such as idelalisib) and/or BCL2 pathway inhibitors (e.g., venetoclax), and were either intolerant to therapy or had relapsed/refractory disease following therapy are also eligible.

### Phase 2a General Inclusion Criteria

1. Patient must have an Eastern Cooperative Oncology Group (ECOG) Performance Score of 0 or 1.
2. Patient must be 18 years or older, of either sex, and of any race.
3. Patient (and/or parent/guardian for patients who otherwise are unable to provide independent consent) must be willing to give written informed consent and be able to adhere to dose and visit schedules.
4. Patient has had prior treatment for lymphoid malignancy requiring treatment for progressive disease/refractory disease (per guidelines for diagnosis and treatment of CLL [2] and revised response criteria for malignant lymphoma [3]).
5. Patient has had  $\geq 1$  prior systemic treatment regimen administered for at least 2 cycles (unless the patient was intolerant or experienced documented progression on therapy) that must have involved either: (1) an anti-CD20 agent (such as rituximab) WITH chemotherapy for B-cell NHL, unless contraindicated in the judgement of the investigator (e.g., the patient was not a candidate for chemotherapy and received ibrutinib as firstline treatment); (2) a cytotoxic chemotherapy drug for T-cell NHL; (3) an anti-CD20 agent (such as rituximab) with chemotherapy for CLL, unless contraindicated in the judgement of the investigator (e.g., the patient was not a candidate for chemotherapy and received ibrutinib as firstline treatment); or (4) in patients with CD30-expressing PTCL, a CD30-directed antibody (e.g., brentuximab vedotin).
6. Female patients of childbearing potential and male patients must agree to abstain from sexual intercourse or to use an effective method of contraception during the study and for 90 days following the last dose of protocol therapy (examples of effective methods of contraception include oral contraceptives or double barrier methods such as condom plus spermicide or condom plus diaphragm). Patients enrolled into Cohort 2 should use effective contraception during treatment with rituximab and for 12 months after the last dose of rituximab.

7. Patient must have adequate bone marrow reserve as evidenced by an absolute neutrophil count (ANC)  $\geq 1,000/\mu\text{L}$ , platelet count  $\geq 75,000/\mu\text{L}$ . Platelet count must be without transfusion support within 7 days of the first dose of cerdulatinib.  
*Note: CLL patients only: ANC  $\geq 750/\mu\text{L}$  and platelet count  $\geq 30,000/\mu\text{L}$  are acceptable. There are no limits on ANC or platelet count required for patients with leukemic forms of PTCL (ATLL, PLL, LGL) or hepatosplenic T-cell lymphoma (HSTCL) as long as cytopenia, if present, is secondary to disease.*
8. Patient must have adequate renal function as evidenced by a creatinine clearance  $\geq 30$  mL/min (calculated using the Cockcroft-Gault equation or based on a 24-hour urine specimen).
9. Patient must have adequate hepatic function as evidenced by a serum bilirubin level  $\leq 2.0$  mg/dL AND serum AST/ALT levels  $\leq 2.5\times$  the ULN for the reference lab. Serum bilirubin  $\leq 2.5$  mg/dL when increase clearly documented as due to Gilbert's syndrome.
10. Where available, ability to submit a formalin-fixed paraffin embedded tissue (FFPE) block or a minimum of 10 unstained, freshly cut FFPE tissue slides from lymph node or other biopsies that were collected as part of patient diagnosis. If samples are unavailable the patient is still eligible for enrollment.
11. Measureable disease for a given tumor type, defined as:
  - a. The presence of  $\geq 1$  lesion that measures  $\geq 1.5$  cm in a single dimension as assessed by CT, CT/PET for patients with nodal or mass lesions (e.g., FL, DLBCL, other NHL), or
  - b. Quantifiable circulating tumor cells for patients with circulating tumor (e.g., Sézary Syndrome [SS]), or
  - c. For CTCL: mSWAT score  $> 0$ .
12. Ability to provide redacted copies of pathology reports and radiology reports used for the diagnosis of NHL or CLL. In addition, for CTCL, ability to provide redacted photographs of skin responses.

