#### 4.4. **Withdrawal Criteria and Replacement of Patients**

Patients are free to withdraw from the study at any time for any reason; however, to the extent possible, all patients should continue to participate in the study once they have enrolled, even if they discontinue study drug. The Investigator also has the right to withdraw a patient from the study in case of events such as inter-current illness, AEs, progression, protocol violation, other procedures needed for treatment of their disease, or other medical conditions, administrative reasons or for other reasons (detailed in Section 4.4.1).

An excessive rate of withdrawals can render the study un-interpretable; therefore, unnecessary withdrawal of patients should be avoided. Should a patient decide to withdraw, all efforts will be made to complete and report the observations as thoroughly as possible. Reasons for all discontinuation of study drug and withdrawals from the study will be recorded. If a patient discontinues the study drug due to an AE, that AE must be evaluated to determine if it is a serious adverse event (SAE; see Section 10.1.2). The Investigator must report all SAEs to the Syneos Safety Department (the Sponsor's Safety Designee) on the SAE form within 24 hours from the point in time when the Investigator becomes aware of the SAE. The procedures described under 30 Days Post-Last Treatment (Section 7.3.2.2) will be performed upon discontinuation/withdrawal, whenever possible. If a patient withdraws consent, no further information will be collected after the study termination visit.

Normal study termination is defined as the 30 Days Post-Last Treatment visit in Section 7.3.2.2.

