### **Cerdulatinib should be taken before the rituximab infusion.**

Rituximab will be administered intravenously (IV) in the clinic. Dosing will be based on mg/m^2 of body surface area (BSA). The dose calculation of BSA will be based on the patient's height and actual body weight prior to therapy. After establishment of BSA based on the patient's pretreatment body weight, do not alter the total dose of rituximab for the patient, despite fluctuations in the patient's body weight.

Rituximab will be administered IV at 375 mg/m^2 on Days 1, 8, 15, and 22 of Cycle 1, and during Cycles 4, 6, 8, and 10 on Day 1 only.

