#### **7.3.2.2. 30 Days Post-Last Treatment**

30 days after the last cerdulatinib dose administered, patients should return to the site for a follow-up visit consisting of a number of safety and response assessments as indicated in [Appendix 1](#).

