#### ***10.2.4.13. Pregnancy Exposure and Birth Events***

If a female study patient becomes pregnant during study drug administration or within 16 weeks after date of last dose, the Investigator should be informed immediately and study treatment must be discontinued if not already terminated. The Investigator must urgently email a completed Pregnancy Form to Syneos Safety Department (Section 10.2).

If a female partner of a male study patient is pregnant or suspects she is pregnant by the male study patient (between study drug administration and up to 16 weeks after the termination visit), the Investigator should be informed immediately. The Investigator must advise the male patient to have his female partner inform her treating physician immediately, and the Investigator must urgently email a completed Pregnancy Report Form to Syneos Safety Department.

In all cases, the pregnancy must be followed up through delivery or other fetal outcome. Newborns should be monitored until at least 8 weeks of age for any potential congenital anomalies. The Investigator should promptly report any abnormal fetal outcome (i.e., congenital anomaly or birth defect, spontaneous or therapeutic abortion, stillbirth, pre-mature birth or outcome other than live normal birth) on an SAE form.

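### In Cohort 2, required pregnancy reporting can end up to 253 days before the protocol's own 12-month post-rituximab contraception period, and the rule does not say which drug's last dose starts its clock

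*Protocol*

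**What the plan says.** Item 6 of the Phase 2a General Inclusion Criteria (Synopsis and Protocol Section 4.1.2) sets two contraception periods. For all patients it runs through the study and "for 90 days following the last dose of protocol therapy". For the rituximab combination cohort it adds: "Patients enrolled into Cohort 2 should use effective contraception during treatment with rituximab and for 12 months after the last dose of rituximab".

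Pregnancy reporting is in Protocol Section 10.2.4.13 and does not vary by cohort. For a female patient the duty applies when she "becomes pregnant during study drug administration or within 16 weeks after date of last dose". For a male patient's partner the window is "between study drug administration and up to 16 weeks after the termination visit". A pregnancy inside the window triggers a Pregnancy Form, follow-up to the outcome of the pregnancy and monitoring of the newborn to at least 8 weeks of age.

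Three other places fix the dates:

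- Section 4.4: "Normal study termination is defined as the 30 Days Post-Last Treatment visit in Section 7.3.2.2".
- Section 7.3.2.2: "30 days after the last cerdulatinib dose administered, patients should return to the site for a follow-up visit". The termination visit is therefore tied to cerdulatinib.
- Section 6.2.3 gives rituximab "on Days 1, 8, 15, and 22 of Cycle 1, and during Cycles 4, 6, 8, and 10 on Day 1 only", whereas Section 3.1.4 sets no fixed end for cerdulatinib.

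The reporting rule does not define the last dose. SAP Section 7.1.1 defines study drug as either cerdulatinib or rituximab, which does not settle the matter for the protocol.

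**The concern.** The contraception rule marks out a period during which the protocol asks Cohort 2 patients to avoid pregnancy. The reporting rule decides which pregnancies the sponsor is told about. In Cohort 2 the second can stop well before the first. The amendment summary records that Amendment 7 brought the Cohort 2 contraception rule into line with the rituximab label; the current reporting section has no corresponding term, and no reason for the difference is given.

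A pregnancy that begins in the gap requires no form, no follow-up to delivery and no newborn monitoring. Nothing else in the protocol supplies these. Study participation ends at the visit 30 days after the last dose (Sections 3.1.3 and 4.4), and Amendment 9 removed long-term follow-up. What is at stake is systematic information on pregnancy outcome after the combination, including the uneventful pregnancies that form the denominator for any adverse outcome.

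**Working it through.** The documents give no figure for this gap, so there is none to reproduce. The check is date arithmetic.

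**Inputs**

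- Cohort 2 contraception: 12 months after the last rituximab dose, taken as 365 days (Section 4.1.2, item 6).
- Reporting, female patient: 16 × 7 = 112 days after the last dose (Section 10.2.4.13).
- Reporting, male patient's partner: termination visit at 30 days, plus 112, = 142 days after the last cerdulatinib dose (Sections 4.4, 7.3.2.2 and 10.2.4.13).
- Cycle length 28 days (Section 7.3.3.1). Rituximab therefore falls on study days 1, 8, 15, 22, 85, 141, 197 and 253; for example, Cycle 10 Day 1 is 9 × 28 + 1 = 253.

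**Both drugs stopped on the same day**

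- Female patient: 365 − 112 = 253 days uncovered; 253/365 = 69%.
- Partner: 365 − 142 = 223 days uncovered; 223/365 = 61%.

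**Clock started at the last cerdulatinib dose**

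Gap = max(0, last rituximab day + 365 − [last cerdulatinib day + 112 or 142]), assuming treatment stops at the end of the stated cycle.

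| Cerdulatinib stops at end of | Last cerdulatinib day | Last rituximab day | Contraception to day | Female: reporting to day | Female: gap | Partner: reporting to day | Partner: gap |
|---|---|---|---|---|---|---|---|
| Cycle 1 | 28 | 22 | 387 | 140 | 247 | 170 | 217 |
| Cycle 6 | 168 | 141 | 506 | 280 | 226 | 310 | 196 |
| Cycle 12 | 336 | 253 | 618 | 448 | 170 | 478 | 140 |
| Cycle 16 | 448 | 253 | 618 | 560 | 58 | 590 | 28 |
| Cycle 18 | 504 | 253 | 618 | 616 | 2 | 646 | 0 |
| Cycle 19 | 532 | 253 | 618 | 644 | 0 | 674 | 0 |

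After the full rituximab course, the gap closes for a female patient once cerdulatinib reaches day 618 − 112 = 506, early in Cycle 19. For a partner it closes at day 618 − 142 = 476, the end of Cycle 17.

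**Clock started at the last rituximab dose**

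This reading is open for female patients because the rule names no drug. In the Cycle 12 case, reporting would run to day 253 + 112 = 365, which is already past the end of cerdulatinib at day 336. The gap would be 618 − 365 = 253 days instead of 170. Time still on cerdulatinib is covered on either reading, because the rule applies during study drug administration. The undefined anchor therefore moves this case by 83 days.

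**The case against.** Four points can be made against this concern.

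First, the gap depends on when cerdulatinib stops. That is correct, and the table shows it. The 69% applies only when both drugs stop together. Counted from the last cerdulatinib dose, the female-patient gap exceeds half of the 12 months only if cerdulatinib ends within about 71 days of the last rituximab dose (365/2 − 112 ≈ 71).

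Second, there is a residual route. A congenital anomaly is a serious adverse event under Section 10.1.2, including where the father was exposed before conception, and Section 10.2.1 keeps late serious events reportable when the investigator judges them related. This also stands. It does not replace pregnancy reporting: the site must learn of the outcome and attribute it to study drug, and uneventful pregnancies are not captured.

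Third, contraception and reporting windows need not be equal. In general they need not. But in the single-agent cohorts reporting for a female patient (112 days) outlasts contraception (90 days), so the whole precaution period is covered. Only in Cohort 2 can the order reverse, and no reason is given.

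Fourth, the point is small. It concerns one cohort of roughly 20 to 50 patients (Section 11.2.2) and touches no efficacy endpoint or planned analysis. That limits its weight but does not answer it.

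A reader might also infer that the 22-day difference in the single-agent cohorts (112 − 90) is a defect. The documents do not support that. Collecting reports for longer than contraception is asked for loses nothing and is a reasonable margin.

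**Conclusion.** The mismatch is real. Followed exactly, the protocol leaves up to 253 of 365 days (69%) for a female Cohort 2 patient, or about 223 days (61%) for a male patient's partner, inside the contraception period but outside required pregnancy reporting. From the last cerdulatinib dose, the female-patient gap is 247 days after a stop at the end of Cycle 1, 170 days after all eight rituximab doses with cerdulatinib to Cycle 12, and zero from about Cycle 19. These figures assume 28-day cycles without delay, rituximab on schedule, stopping at the end of a cycle and a termination visit exactly 30 days after the last cerdulatinib dose.

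A reader might go further and infer that most pregnancies in the period would never be reported. The documents do not support this. They give no pregnancy rate, timing or number of patients of childbearing potential, so a share of days cannot be read as a share of pregnancies. Never is also too strong, because birth defects and other late serious events judged related remain reportable. Nor is the contraception text worded as an absolute obligation: it says patients should use contraception, not that they must.

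This is a cheap, worthwhile safety correction rather than a threat to the trial's conclusions.

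**What to change.** Reconcile item 6 of Section 4.1.2 (and its copy in the Synopsis) with Section 10.2.4.13 in two respects:

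- Give the reporting rule a Cohort 2 term, so that required reporting and follow-up of pregnancies in patients and partners cover the contraception period the protocol itself sets for that cohort. Tying the term to item 6 by reference would keep the two from drifting apart again.
- State which drug's last dose starts the window for a female patient in the combination cohort.

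This takes no position on which contraception period is right; it asks only that reporting match it. The single-agent windows need no change on this account.

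The cost is a sentence or two in Section 10.2.4.13 and matching safety-plan and site instructions, with no added visit or test. The downside is a longer passive duty for Cohort 2 sites after the 30-day visit, including follow-up to delivery and of the newborn for any pregnancy reported late. With no scheduled contact by then, reporting would depend on patients volunteering the information. The present rule already relies on this, since its 16-week window also extends past the 30-day visit.

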#### Phase 2a Cohort-Specific Inclusion Criteria

- Cohort 1 (FL): Grades 1 to 3A (Single-Agent Cerdulatinib): Received  $\geq 1$  prior treatment regimen.
- Cohort 2 (Combination): FL, Grades 1 to 3A (Cerdulatinib + Rituximab): Received  $\geq 1$  prior treatment regimen.
- Cohort 3 (aNHL): aNHL (Single-Agent Cerdulatinib): Aggressive non-Hodgkin lymphoma (aNHL) is defined as DLBCL, FL Grade 3B, Mantle Cell Lymphoma (MCL), and transformed NHL. Patients had relapsed from  $\geq 1$  but  $\leq 3$  prior cytotoxic chemotherapy regimens with an anti CD20 antibody, (e.g., R-CHOP, BR). Patients must have received an anthracycline based therapy unless anthracyclines were deemed inappropriate in the judgement of the investigator. Patients must have either relapsed following autologous stem cell therapy (ASCT), or not be candidates (ineligible) for ASCT, defined as meeting any of the following criteria [1]: a) Age  $\geq 70$  years; b) DLCO  $< 50\%$  by pulmonary function tests; c) FEV1/FVC  $< 60\%$  predicted by pulmonary function tests; d) LVEF  $< 45\%$  by MUGA or echocardiogram; e) uncontrolled arrhythmia; f) calculated creatinine clearance (Cockcroft-Gault)  $\leq 60$  mL/min; g) other comorbidities (e.g., medical conditions or psychosocial conditions) that would likely result in an unacceptably high probability of treatment/transplant related morbidity and mortality in the judgement of the investigator (e.g., high HCT-CI, CIRS, scores); h) Refusal of ASCT.
- Note: Antibody drug conjugates (ADC) count as cytotoxic chemotherapy. Salvage chemotherapy prior to ASCT with or without maintenance therapy counts as one regimen.
- Cohort 4 (CLL/SLL): CLL/SLL (Single-Agent Cerdulatinib): Received  $\geq 1$  prior treatment regimen.
- Cohort 5 (PTCL NHL): Peripheral T-cell NHL (PTCL) (Single-Agent Cerdulatinib): Received  $\geq 1$  prior systemic treatment regimen for PTCL. In patients with CD30-expressing PTCL, prior treatment must include a CD30-directed antibody (e.g., brentuximab vedotin).
- Cohort 6 (CTCL NHL): Cutaneous T-cell NHL (CTCL, MF/SS only) (Single-Agent Cerdulatinib): Received  $\geq 1$  prior systemic treatment regimen for CTCL.

#### Phase 1 and Phase 2a Exclusion Criteria

A patient meeting any 1 of the Exclusion Criteria listed below will be excluded from the trial, whether enrolled in Phase 1 or Phase 2a of the study.

1. Patient has Richter's syndrome, Burkitt's lymphoma, or Burkitt-like Lymphoma. Patients with transformed DLBCL from Follicular NHL are eligible.
2. Patient has undergone prior allogeneic or autologous transplant with infusion of stem cells within 90 days before Cycle 1 Day 1 (C1D1), or on active immunosuppressive therapy for graft-versus-host disease (GVHD) or GVHD prophylaxis within 8 weeks before C1D1.
3. Patient has received prior therapy with a spleen tyrosine kinase (SYK) inhibitor.
4. Patient requires chronic treatment with a strong CYP3A4 inhibitor or inducer or CYP3A4-sensitive substrate ([Appendix 3](#)).
5. Patient has known lymphomatous involvement of the central nervous system (CNS).
6. Patient has a known hypersensitivity to any of the components of cerdulatinib.
7. Patient has persistent, unresolved NCI CTCAE v5.0  $\geq$  Grade 2 clinically significant (in the judgement of the investigator) drug-related toxicity (except alopecia, erectile impotence, hot flashes, libido, neuropathy) associated with previous treatment.
8. Prior monoclonal antibody (Mab) (including alemtuzumab), radioimmunoconjugate, antibody drug conjugate (ADC), phototherapy, radiotherapy, chemotherapy, immunotherapy, immunosuppressive therapy, or any investigational agent for the purposes of treating cancer within 3 weeks before Cycle 1 Day 1.
9. For CTCL patients only: total skin electron beam therapy (TSEBT) within 12 weeks, or initiation of topical steroid, nitrogen mustard, or topical retinoid within 2 weeks before Cycle 1 Day 1. Patients with CTCL who are on a stable topical regimen for  $\geq$  4 weeks prior to C1D1 are allowed.
10. The patient has a known infection with HIV, hepatitis B virus (HBV), or hepatitis C virus (HCV) or is a carrier of HBV or HCV. Patients who are seropositive for HCV antibody must test negative for HCV by polymerase chain reaction (PCR) assay to be eligible. Patients with an occult or prior HBV infection (defined as being seropositive for total hepatitis B core antibody [HBcAb] and seronegative for HBsAg) may be included if his or her HBV DNA is undetectable or if it is undetectable with antiviral therapy. These patients must be willing to undergo additional testing per local standard of care if this data is unavailable. Additional testing will be performed if the patient does not have documentation of a negative hepatitis panel and negative HIV history within the 12-week period prior to enrollment.
11. Patient has an active infection requiring systemic treatment, defined as requiring antimicrobial, antifungal, or antiviral agents. Prophylactic antimicrobial treatment is permitted.
12. Patient has significant gastrointestinal disease that may interfere with absorption of the study drug or that predisposes him/her to GI adverse effects, or has had major gastric or bowel surgery.
13. Patient has difficulty swallowing or malabsorption syndrome.
14. Patient has any other medical, social, or psychiatric condition that might interfere with the patient's participation in the trial or interfere with the interpretation of trial results.
15. Patient has undergone major surgery within 4 weeks prior to first study drug administration.
16. Patient has a history (within 2 years prior to first study drug administration) of another malignancy unless malignancy treated with curative intent and likelihood of relapse is small ( $< 5\%$  in 2 years in the judgement of the investigator). Patients with a history of squamous or basal cell carcinoma of the skin or carcinoma in situ of the cervix may be enrolled.
17. Patient is receiving systemic steroids at doses greater than the equivalent of prednisone, 20 mg daily, with the exception of intermittent use for the treatment of emesis.
18. Patient is female and is breast-feeding, pregnant, or intends to become pregnant.
19. Patient is participating in any other therapeutic clinical study (observational or registry trials are allowed).

